8.3.3.5 Engraftment

Engraftment of transduced cells will be assessed over time using vector gene marking in peripheral blood cells (PBMC, granulocytes, T-cells, B-cells, NK cells, myeloid cells). The vector copy numbers in each type of cell will be summarized using descriptive statistics. In addition, for each cell type, plots of the median and range over time on a logarithmic scale will be produced along with individual subject plots.

8.3.3.6 ADA Expression, Enzyme Activity and Detoxification

RBC ADA activity, deoxyadenine nucleotides, AXP, dAXP and %dAXP will be summarized by visit. The median value and range will be plotted over time on a logarithmic scale as will the values for individual subjects. Deoxyadenine nucleotide evaluations that are 'undetectable' will use the limit of quantitation in the summary.

ADA activity and deoxyadenine nucleotides in erythrocytes will also be categorized as normal/abnormal, not clinically significant/abnormal clinically significant. The number (%) of subjects with evaluations in each category will be summarized by visit.

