1.1.2.1 Hematopoietic Stem Cell Transplantation

Hematopoietic stem cell transplantation from allogeneic human leukocyte antigen (HLA)-compatible sibling donors is the treatment of choice for patients with SCID and other severe variants of primary immunodeficiency resulting in long-term survival of about 90% of patients and effective immune reconstitution ([Ferrua 2010](#)). However, as only 10–20% of patients are able to receive HSCT from an HLA-identical family member ([Stephan 1993, Antoine 2003](#)), transplants are often performed from mismatched family or matched unrelated donors (MUD). Despite improvements in pre-conditioning and post-transplant care, the use of less well matched HSCT is associated with reduced survival ([Gaspar 2009, Hassan 2012](#)) and delayed or suboptimal immune reconstitution in a significant fraction of surviving patients as a result of poor early engraftment or gradual decline in immune functions ([Railey 2009](#)). Complications such as Graft versus Host Disease (GvHD), autoimmune and inflammatory manifestations, persistent infections, and disease-related issues are often observed.

If a matched sibling/family donor is unavailable, most ADA-SCID patients are treated with ADA ERT. Enzyme replacement therapy leads to metabolic correction and clinical

improvement, but the immunological reconstitution is often incomplete and dysregulated (Hershfield 1987, Gaspar 2009, Sauer 2012) and therefore individuals remain at risk of severe infection. This approach does not represent a curative treatment modality and is not always available as a long-term option. Enzyme replacement therapy with polyethylene-glycol (PEG)-ADA was developed based on the concept that reduction of ADA substrate concentration in plasma results in lowering of intracellular concentrations of metabolites (Hershfield 1995). An intramuscular injection of PEG-ADA is administered weekly or bi-weekly, and is considered to be an excellent (although very expensive) short-term measure to stabilize children with ADA-SCID; however, prolonged use has associated risks as described in the IB.

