For subjects who have successfully received the OTL-101 product, PEG-ADA ERT use will be evaluated at the 1 Month follow-up visit (30 days post treatment ± 7 days) and discontinued at Day 30 (-3/+15) after the transplant. Hematologic reconstitution will be assessed at Day 42 (± 7 days), and in the event of no reconstitution the backup HSC sample will be administered, if the investigator believes this is in the subject's best interest. The subjects will then be seen at regular intervals to review their history, perform examinations and draw blood samples at Months 3, 6 and 9 (all ± 2 weeks) as well as Months 12, 18 and 24 (all ± 4 weeks). Any medically-indicated interventions, including the need to reinstate PEG-ADA ERT, will be assessed at all follow-up visits after Month 1. Hematopoietic reconstitution will be assessed again at the Month 6 visit and if there is still no evidence of cellular recovery, the subject will be given ERT and/or HSCT, if available and deemed appropriate by the Investigator. After the Month 24 visit, the subjects will have completed the study and may enter a long term registry.

This study will include three statistical analyses:

1. The first analysis will compare the success/failure data 6-months post OTL-101 infusion between fresh and cryopreserved OTL-101 formulations. The success/failure of OTL-101 will be defined by the three criteria listed in the primary objectives ([Section 2.2.1](#)). This data will be compared with available data from one of the ongoing Phase I/II studies using the OTL-101 fresh formulation. This will support the CMC comparability data between OTL-101 cryopreserved and fresh formulations. Secondary and exploratory endpoints will also be described.
2. The second analysis will determine the 12 month overall survival and event free survival for all subjects. Secondary and exploratory endpoints, as well as baseline characteristics, subject disposition, and safety data will also be described.
3. The third and final analysis will be performed to determine the overall survival and event free survival for all subjects 24 months post OTL-101 infusion. Secondary and exploratory endpoints, as well as baseline characteristics, subject disposition, safety and Busulfan pharmacokinetic (PK) data will also be described.

Efficacy analyses will be primarily descriptive in nature.

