6.1.2 Rescue Administration of Autologous HSC Backup

If a subject has not achieved hematopoietic reconstitution at Day 30 (Month 1 visit), he/she will be closely monitored as per standard medical management in order to determine the need for a rescue administration of the autologous back-up. A rescue administration will be given according to the physician's criteria if reconstitution is not observed by Day 42. Subjects may receive transfusions to give more time to observe whether signs of hematopoietic reconstitution are seen. This is not documented in the Schedule of Events tables as rescue procedures would follow standard institute protocols.

- A failure of hematologic reconstitution is defined as persistent ANC < 200/ μ l or platelets < 20,000/ μ l on three independent and consecutive determinations over at least ten days after day 42 from the day of OTL-101 infusion.

If these conditions are fulfilled, the subject's autologous back-up cells will be infused according to standard institute protocols.

If, at Day 90 from the initial infusion of OTL-101, a failure of hematologic reconstitution persists after the subject's autologous back-up cells have been infused and the subject is experiencing prolonged unresponsive pancytopenia, the subject will be withdrawn from the study.

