All subjects included in the study will receive PEG-ADA (Adagen®) prior to OTL-101 infusion, which will be continued until Day 30 (+/-3 days) post-transplant. If, at Day 30 (+/-3 days) post infusion of OTL-101, the subject is not suffering from active infections or other major medical problems, PEG-ADA administration will be discontinued.

2. Rules for re-starting ERT or plan allogenic HSCT (if available)

If, by 6 months after the OTL-101 infusion, there is no evidence of hematopoietic reconstitution following the infusion of the back up OTL-101 and rescue medication/treatment, subjects will require rescue PEG-ADA or allogenic HSCT if available. Positive evidence of hematopoietic reconstitution will require:

- a. RBC ADA >0 Units,
- b. absolute CD3+ T-cell counts $\geq 200/\text{mm}^3$, and
- c. peripheral blood samples positive for vector sequences by qPCR ($>1/10,000$ cells).

In addition, PEG-ADA may be re-started if the Investigator deems it in the best interests of the subject on clinical grounds, e.g. multiple, serious or unresponsive infections or sub-normal immune reconstitution. Once ERT has been re-started, the subject will remain in the study and will continue to be followed-up. If the subject fails to demonstrate hematopoietic reconstitution and has the possibility of receiving an allogeneic transplant, the subject should be withdrawn from the study in order to follow institute transplantation protocols.

Once re-started, PEG-ADA may be discontinued if all the following criteria are met: no active infection, PBMC ADA >6 Units, absolute CD3+ T-cell counts $\geq 200/\text{mm}^3$, and peripheral blood samples positive for vector sequences by qPCR.

Prophylaxis for Infections

Prophylactic antimicrobial agents will be used to provide coverage for *Pneumocystis jirovecii* pneumonia and mucosal yeast:

- *Pneumocystis jirovecii* prophylaxis (PJP): Trimethoprim/sulfamethoxazole (TMP/SMX), which will be stopped prior to CD34+ cell harvest and then resumed when ANC >500 . If, after Day 30, ANC is <500 , an alternative PJP prophylaxis regimen will be used. Suitable alternative PJP prophylactic medications include pentamidine (intravenous or aerosolized) or atovaquone. Dapsone should be used with caution,

because of its potential myelosuppressive effects. PJP prophylaxis can be discontinued when CD4 >200/ μ l ([Griffith2009](#)).

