The levels of deoxyadenine nucleotides in erythrocytes will be determined at each time point (at the laboratory headed by [name], Duke University). The level of deoxyadenine nucleotides in erythrocytes provides an indirect assessment of systemic detoxification by ADA enzyme activity. While not a primary study endpoint, this parameter will be measured to provide additional information on the effects of the procedure.

Quality of Life

An assessment will be made of general quality of life and neurological development according to the schedule of events tables. During these visits, the impact of illness on health-related quality of life will be determined using the Karnofsky/Lansky performance scale (which is recommended for immune deficiencies and transplanted patients) (see [Section 17: Appendix 2](#)).

Questions relevant to general well-being, school attendance and ability to practice sports, will also be posed to the subject and his/her parents/legal guardians by the Investigator. These questions will form part of the eCRF. Questions suitable/relevant to the age of the subject will be posed.

Infections

Although infections are safety evaluations, in ADA-SCID, they are also a clear feature of the disease. Evaluation of the frequency of severe infections or opportunistic infectious episodes is an important measure to evaluate efficacy (immune-reconstitution). This is defined as infections or severe infections requiring hospitalization or prolonging hospitalization and/or documented infections by opportunistic pathogens (e.g. interstitial pneumonia, intractable diarrhoea).

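### Erythrocyte dAXP is summarised and classified by visit without regard to PEG-ADA restart, so on-drug values can be read as detoxification by the gene therapy

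*SAP*

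**What the plan says.** SAP 8.3.3.6 gives the whole analysis of these markers: "RBC ADA activity, deoxyadenine nucleotides, AXP, dAXP and %dAXP will be summarized by visit", and "The median value and range will be plotted over time on a logarithmic scale as will the values for individual subjects". The same section classifies ADA activity and deoxyadenine nucleotides as normal or abnormal and reports the number and percentage in each class by visit. Neither it nor any other SAP section has a rule for values taken on PEG-ADA or after a red-cell transfusion.

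Protocol 7.2 explains what dAXP is for: "The level of deoxyadenine nucleotides in erythrocytes provides an indirect assessment of systemic detoxification by ADA enzyme activity".

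On PEG-ADA, the protocol says:
- 1.1.2.1, on the rationale for the drug: "reduction of ADA substrate concentration in plasma results in lowering of intracellular concentrations of metabolites".
- 6.2.1.1: "All subjects included in the study will receive PEG-ADA (Adagen®) prior to OTL-101 infusion".
- 3.1: it is then "discontinued at Day 30 (-3/+15) after the transplant". Section 6.2.1.1 gives a window of 3 days either side instead.
- 6.2.1.1, on restart on clinical grounds: "Once ERT has been re-started, the subject will remain in the study and will continue to be followed-up".

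On transfusion, Protocol 5.1.2 allows 10 to 15 cc/kg of packed red cells after the marrow harvest. Protocol 6.1.2, on slow reconstitution, adds: "Subjects may receive transfusions to give more time to observe whether signs of hematopoietic reconstitution are seen". It does not say of what.

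**The concern.** Erythrocyte dAXP is measured to show that ADA produced by the corrected cells is clearing toxic metabolites. By the protocol's own account, PEG-ADA clears them too. Once a subject is back on PEG-ADA, a low dAXP no longer shows that the gene therapy is working, and restart is itself a failure under event-free survival. Yet that low value enters the by-visit table, the plotted range, the percentage classed as normal and an unmarked individual curve on the same footing as a value from a subject free of the drug.

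The consequence is not purely descriptive. SAP section 6 says that at the first analysis the exploratory endpoints will be compared with the fresh-formulation study in support of comparability. A difference in PEG-ADA exposure between the two groups could look like a formulation difference, or hide one.

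The SAP does take replacement therapy into account elsewhere: under 8.3.2.5, tetanus antibodies are measured only in subjects who have stopped immunoglobulin.

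**Working it through.** The plan states no figure for these summaries. Its one precision figure, 15% for 10 of 10 successes (Protocol 9.4), reproduces: the exact lower limit is 0.025^(1/10) = 0.6915 and the half-width is (1 − 0.6915)/2 = 0.154. It does not bear on this point.

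**1. Who contributes on-drug values after Month 1.** Protocol 6.2.1.1 retains restarters. Protocol 5.1.7 (Month 6) and SAP 5.1 withdraw Month 6 non-responders. Even with those withdrawals, three sources remain: restarts before Month 6, later restarts in Month 6 responders, and early-termination samples, which under Protocol 5.1.8 include ADA and deoxyadenine nucleotides.

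**2. How likely a restart is.** Protocol 1.3.3 reports 93.3% event-free survival in the second fresh study, with one subject clinically indicated to restart: 1 − 0.933 = 6.7%. The first fresh study had no restart in 18. Restart risk p in this trial is therefore an assumption, taken here as 3.3% (about half of 6.7%) to 10%. The chance of at least one restart in 10 is 1 − (1 − p)^10:

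| p | Calculation | Chance |
|---|---|---|
| 3.3% | 1 − 0.967^10 | 0.29 |
| 6.7% | 1 − 0.933^10 | 0.50 |
| 10% | 1 − 0.900^10 | 0.65 |

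**3. Weight of one subject.** 1/10 = 10 percentage points at full enrolment. At the first analysis, which needs a minimum of five subjects (SAP section 6), it is 1/5 = 20 points.

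**4. Which statistics move.** The documents contain no dAXP values, so this is an illustration with assumed ones. Subjects who remain corrected have values rising from 1.0 in steps of 0.5. A restarter would have 30 off the drug and has 3 on it. A value of 6 or less counts as low.

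| Restarters | Median, off drug → on drug | Maximum, off → on | Low of 10, off → on | Low if restarters are set aside |
|---|---|---|---|---|
| 1 | 3.25 → 3.0 | 30 → 5 | 9 → 10 | 9 of 9 |
| 2 | 3.25 → 3.0 | 30 → 4.5 | 8 → 10 | 8 of 8 |
| 3 | 3.25 → 3.0 | 30 → 4 | 7 → 10 | 7 of 7 |

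The median hardly changes. The maximum and the low count change completely. The median moves materially only with many restarters: with five it goes from 16.5 to 3.0, but five or more has probability 0.0003 at p = 6.7% and 0.0016 at 10%. The last column shows that setting restarters aside also yields 100% low, so an exclusion is informative only if the number excluded is reported.

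**5. ADA activity and donor red cells.** Protocol 7.2 refers to a reference range for erythrocyte ADA in normal donors, so transfused red cells can carry ADA. Table 1 puts harvest about 30 days before infusion and baseline at Day −10 to −4. Baseline is then −10 + 30 = 20 to −4 + 30 = 26 days after a harvest transfusion, and Protocol 5.1.3 lets the baseline ADA sample in younger subjects be drawn any time between harvest and infusion. If donor cells persist for up to 120 days (assumption), they can be present until −30 + 120 = Day 90. At half that, 60 days, the limit is Day 30. The baseline sample falls inside either window; Month 3 is reached only near the longer one.

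**The case against.** Several stronger readings are tempting, and the documents do not support them.

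- **That baseline and Month 1 contaminate the later course.** All subjects are on PEG-ADA at baseline and stop around Month 1, but the summaries are by visit, so these points stay apart from Month 3 onward. SAP 8.3.3.6 plans no change from baseline. A baseline lowered by PEG-ADA would make later improvement harder to show.
- **That treatment failures in general stay in and look detoxified.** Month 6 non-responders are to be withdrawn (Protocol 5.1.7 and 7.1.1, SAP 5.1), and Protocol 6.2.1.1 withdraws a subject without reconstitution who can have an allogeneic transplant. Only the groups in step 1 of the working are affected.
- **That PEG-ADA raises red-cell ADA activity.** Protocol 1.1.2.1 speaks of metabolites only.
- **That red cells are transfused after Busulfan.** Protocol 6.1.2 leaves the type of transfusion unstated, and failure of reconstitution is defined there by neutrophils or platelets.
- **That later medians are improved by failures.** The illustration shows little effect with one to three restarters.

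It is also fair to say that these are exploratory, descriptive summaries, that Protocol 7.2 itself says deoxyadenine nucleotides are not a primary endpoint, that restart counts as an event in event-free survival, and that individual plots and a listing of concomitant medications are planned. With ten subjects a careful reader could join these up. That limits the importance of the point but does not remove it: the table of percentages and the comparison with the fresh study would still carry unmarked on-drug values.

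Finally, making exclusion the main analysis would be worse. It would drop failures from the all-treated efficacy population of SAP 7.1 and leave a selected group.

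**Conclusion.** The point holds in a limited form. SAP 8.3.3.6 lets dAXP values taken after a PEG-ADA restart count as detoxification in the range, the normal/abnormal percentages and the individual curves. The effect is up to 10 percentage points per restarter at N=10, and the chance of at least one restart is 0.29 to 0.65 if the risk is 3.3% to 10%. That risk is an assumption drawn from small fresh-formulation studies, one of which had no restart at all. The median is little affected in the illustration, and the true size cannot be known without dAXP values.

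For ADA activity the concern is confined to donor red cells. The documented route is the optional harvest transfusion before baseline; later transfusion is possible but its type is not stated.

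The sections that retain restarters (Protocol 6.2.1.1) and those that withdraw Month 6 non-responders (Protocol 5.1.7, SAP 5.1) conflict where the two groups overlap and must be reconciled, because they determine which samples exist. This is a worthwhile improvement to an exploratory analysis and does not threaten the survival endpoints.

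**What to change.** Amend SAP 8.3.3.6 as follows.

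1. For every ADA and dAXP sample, including baseline, derive PEG-ADA status and days since the last recorded red-cell transfusion.
2. Keep the all-values by-visit table, with its normal/abnormal counts, for the efficacy population.
3. Add a by-visit summary with the same counts, limited to post-Month 1 samples taken off PEG-ADA, before any rescue HSCT and outside a pre-specified post-transfusion window. State that 120 days is an assumption and show the result with a shorter window. Report at each visit how many values were left out and why.
4. Mark PEG-ADA periods and transfusions with distinct symbols on the individual plots.

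Separately, reconcile the retention and withdrawal rules named above.

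The cost is SAP wording and two derived variables. PEG-ADA use is already recorded at each follow-up visit (Protocol Table 2), concomitant therapy is entered in the eCRF (Protocol 6.2), and harvest transfusion is already summarised under SAP 8.2.12. The drawback is a smaller and selected group in the added summary, which is why it supplements the full table and does not replace it.

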8.3.3.7 Vector Integration Analysis

The number (%) of subjects with one integration site representing > 30% of total integration will be summarized by visit. The number (%) of subjects for whom one integration site contributed > 30% of total integration at two or more time points will also be summarized. In addition, the total number of integration sites will be summarized by visit.

8.4 Safety Evaluations

8.4.1 Adverse Events

All adverse events will be coded using MedDRA version 20.0 or higher.

8.4.1.1 Definition of Treatment-emergent Adverse Events

Adverse events (AEs) will be summarised on the basis of treatment emergence. An adverse event is considered to be treatment emergent if it occurred on or after the date and time of the

start of the IMP infusion. If the start time of the event is not present, any event starting on the same day as the infusion will be considered to be treatment emergent. If the start date of the adverse event is partial or missing, it will be considered to be treatment emergent if:

- the day is missing, the month and year are present and are the same as or after the month and year of the infusion and the end date is missing or is not before the date of infusion,
- the day and month are missing, the year is present and is the same as or after the year of the infusion and the end date is missing or is not before the date of infusion,
- the entire date is missing and the end date is missing or is not before the date of infusion.

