8.2 Safety Assessments

8.2.1 Adverse Events

Adverse events will be monitored and recorded from the time that the subject's parents/legal guardians provide informed consent and then throughout the study (see [Section 3.5](#) for definition of the study duration) and will be elicited by direct, non-leading questioning or if spontaneously reported by the subject/parent/legal guardian. Further details on AE reporting can be found in [Section 8.2.2](#).

An AE is the development of an undesirable medical condition or the deterioration of a pre-existing medical condition following or during exposure to a pharmaceutical product, whether or not it is considered to be causally related to the product. An undesirable medical condition can be symptoms (e.g. nausea, chest pain), signs (e.g. tachycardia, enlarged liver) or the abnormal results of an investigation (e.g. laboratory findings, ECG). In clinical studies an AE can include an undesirable medical condition occurring at any time, including run in or washout periods, even if no OTL-101 has been administered.

Death due to disease progression will be recorded as part of the efficacy evaluation (due to failure of the OTL-101 product) and will be regarded as an SAE unrelated to OTL-101.

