8.2.2 Recording and Follow up of Adverse Events

At each study visit, the subject (or parent/legal guardian) should be asked a non-leading question such as: "How have you felt since transplantation (or last visit)?" All observed or voluntarily reported AEs, regardless of their potential causal relationship with OTL-101, will be recorded on the AE page(s) of the eCRF. Events involving drug reactions, accidents,

illnesses with onset during the study, or exacerbations of pre-existing illnesses should be recorded. Any AEs already recorded and designated as 'continuing' should be reviewed at each subsequent assessment.

Any AEs reported at visits to the subject's general practitioner must be transmitted by the healthcare professional to the responsible investigational site staff, if possible on the same day, so that they can be recorded in the eCRF, notified to the Sponsor (if an SAE), and followed up appropriately by the responsible investigational site staff.

For all AEs, the Investigator must pursue and obtain information that is adequate both to determine the outcome of the AE and to assess whether it meets the criteria for classification as an SAE requiring immediate notification to the Sponsor or its designated representative. For all AEs, sufficient information should be obtained by the Investigator to make an assessment of the causality of the AE (i.e. protocol treatment or other illness). The Investigator is required to assess causality and record that assessment on the eCRF. Follow up of the AE, after the date of OTL-101 infusion, is required if the AE or its sequelae persist. Follow up is required until the event or its sequelae resolve or stabilize at a value acceptable to the Investigator and the Sponsor's clinical monitor or his/her designated representative.

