9.6.5 Safety Analyses

All AEs will be coded according to the current Medical Dictionary for Regulatory Activities (MedDRA) version and will be classified by MedDRA preferred term and system organ class. AE listings will be presented by subject, system organ class and preferred term. Incidence of treatment emergent AEs (TEAE) and SAEs will be tabulated by system organ class and preferred term. In addition, summary tables will be presented by maximum severity, relationship to treatment and TEAEs associated with premature withdrawal from the study.

A TEAE is defined as any AE that occurs during the active phase of the study if:

- it was not present prior to receiving the OTL-101 infusion, or
- it was present prior to receiving the OTL-101 infusion but the intensity increased during the active phase of the study, or
- it was present prior to receiving the OTL-101 infusion, the intensity is the same but the drug relationship became related during the active phase of the study.

Summary statistics (mean, median, SD and range as appropriate) will be presented for vital signs, ECG parameters and clinical laboratory tests at each assessment along with change from baseline. For laboratory data, abnormal values will be flagged in the data listings. Shift tables will be presented of the number and percentage of subjects with low, normal or high values and normal or abnormal examinations at each visit and overall.

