8.4.1.2 Adverse Events

Treatment emergent adverse events will be summarized in an overall summary presenting the number (%) of subjects with:

- any AE,
- AE grade 2 or higher (at least moderate in severity),
- AE grade 3 or higher (at least severe in severity),
- treatment related AE,
- AE related to autoimmunity,
- AE leading to study discontinuation,
- any serious adverse event (SAE),
- treatment related SAE,
- SAE related to autoimmunity,
- SAE leading to death.

Incidence and frequency of treatment emergent AEs will be summarised by system organ class (SOC) and preferred term (PT):

- overall,
- by maximum severity,
- treatment related AEs,
- SAEs (if sufficient events),
- AEs leading to study discontinuation (if sufficient events).

In addition, a summary table for the most frequently reported treatment emergent adverse events (those reported in 2 or more subjects) will be presented by PT in descending order of incidence and frequency.

In each table, if the same SOC or PT is reported on multiple occasions for a single subject, it will only be included once in the summary. In the table by maximum severity, only the most severe occurrence for each SOC and PT for each subject will be included in the summary. In the table by maximum relationship, only the most related occurrence for each SOC and PT for each subject will be included in the summary.

Any adverse events that are not treatment emergent (occurred prior to the infusion) will be listed.

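### The SAP's treatment-emergent rule omits the protocol's worsening and became-related limbs, so a pre-infusion AE updated in place can be missing from the AE tables

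*SAP*

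**What the plan says.** **Protocol 9.6.5** gives three routes to treatment emergence, all tied to the active phase of the study. The first is an AE not present before the infusion. The second reads: "it was present prior to receiving the OTL-101 infusion but the intensity increased during the active phase of the study, or" the third, which is an AE present before infusion where "the intensity is the same but the drug relationship became related during the active phase of the study". Incidence tables are then built on treatment-emergent AEs.

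**SAP 8.4.1.1** has one route: "An adverse event is considered to be treatment emergent if it occurred on or after the date and time of the" start of the infusion. Its other sentences deal only with a missing start time on the day of infusion and with partial or missing start dates. Worsening and relationship do not appear.

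**SAP 8.4.1.2** builds the overall summary, the system organ class and preferred term tables, and the frequent-AE table on treatment-emergent AEs. For the rest: "Any adverse events that are not treatment emergent (occurred prior to the infusion) will be listed".

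**Recording.** Protocol 8.2.1 includes in its definition of an AE "the deterioration of a pre-existing medical condition following or during exposure to a pharmaceutical product". Protocol 8.2.2 says that "exacerbations of pre-existing illnesses should be recorded", and that AEs already marked as continuing "should be reviewed at each subsequent assessment". Neither section says whether a worsening opens a new record or updates the existing one.

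**The concern.** The two documents define the same analysis set differently, and the SAP gives no reason for being narrower. Protocol 9.6.1 leaves full statistical methods to the SAP, so the narrower rule is the one likely to be programmed. The resulting tables would not be those that the protocol describes. The summary of changes for Amendment 2 places the three-limb definition among the edits meant to align the protocol with the SAP, so the difference does not look intended.

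The situation is plausible in this trial. AEs are collected from consent (Protocol 5.1.1 and 8.2.1), through marrow harvest and Busulfan conditioning on Days -4 to -1 (Protocol 5.1.4). Some AEs may therefore be ongoing at infusion. If one of them gets worse afterwards, the worsening is post-infusion safety information that the protocol wants counted.

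**Working it through.** The documents give no figure to reproduce, because the point concerns a definition. The check applies both rules to the same records.

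**Inputs.** Protocol 9.6.5 (three limbs); SAP 8.4.1.1 (start on or after infusion, with date rules); SAP 8.4.1.2 (tables and listing); SAP 7.2 (safety population is all treated subjects); Protocol 9.4 (ten treated subjects planned). The dates and grades below are assumed for illustration.

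**Step 1: does the SAP's word for occurrence mean onset?** Yes. The next sentence of SAP 8.4.1.1 speaks of events starting on the day of infusion, and SAP 8.4.1.2 describes non-emergent AEs as those that occurred before it.

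**Step 2: apply both rules.**

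| Record (fully dated) | Protocol 9.6.5 | SAP 8.4.1.1 |
|---|---|---|
| a. Starts Day -2, Grade 1; raised to Grade 3 on Day +5, same record | Emergent (limb 2) | Not emergent; listed only |
| b. Starts Day -2, same grade; later judged related | Emergent (limb 3) | Not emergent; listed only |
| c. Worsening entered as a new record starting Day +5 | Emergent | Emergent |
| d. New AE starting Day +5 | Emergent (limb 1) | Emergent |

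The rules disagree on (a) and (b) only. The SAP's sole extension does not help, because it covers incomplete start dates. It also gives an odd contrast: an AE with no start date at all that is still ongoing at infusion counts as emergent, while the fully dated record (a) does not.

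**Step 3: effect on an any-occurrence row.** Let k be the number of subjects whose only event in that row is of type (a) or (b). The protocol percentage minus the SAP percentage is k/10:

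- k = 0: 0 points
- k = 1: 1/10 = 10 points
- k = 2: 2/10 = 20 points
- k = 3: 3/10 = 30 points

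**Step 4: effect when the subject has another treatment-emergent AE.** The any-occurrence row does not move, but other outputs can. Suppose one subject has a new Grade 1 event and a record of type (a), now Grade 3, under the same preferred term. The protocol rule puts the subject at maximum Grade 3 and the SAP rule at Grade 1. The SAP tables also report frequency; if that counts events, it falls from 2 to 1.

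**Step 5: frequent-AE table.** The SAP plans "a summary table for the most frequently reported treatment emergent adverse events (those reported in 2 or more subjects"). A term with 2 subjects under the protocol definition, one of them only through worsening, has 2 - 1 = 1 subject under the SAP and drops out.

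**The case against.** The strongest reply is that site recording would usually close the gap. Clinically significant changes in examination findings (Protocol 8.2.1.5), vital signs relative to baseline (8.4) and laboratory values relative to pre-harvest tests (8.6) are to be recorded as AEs, and changes in intensity at body-system review go into the eCRF (8.3). Together with the AE definition, this favours entering a post-infusion change as an AE, and the SAP counts it if it carries a post-infusion start date. This part stands: it narrows the gap mainly to symptomatic AEs updated in place. It does not close it, because none of these sections requires a new record.

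A second reply is that little depends on these tables. The study is a single cohort of ten, not powered for significance, and the listings can be read in full. Laboratory worsening appears in the baseline-to-minimum and baseline-to-maximum shift tables (SAP 8.4.6), and the severe-infection rate (SAP 8.3.2.4) applies no treatment-emergent filter. This also stands, and it limits the consequence. Cover is thinner for other symptoms in the first weeks: from Day 1 to Day 24 the scheduled assessments are interval history, hematology and biochemistry (Protocol 5.1.6), so the AE tables are the main graded summary there.

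A third reply is that an instruction to open a new record at each post-infusion grade increase would be enough. It would restore the second limb in practice. It would leave the third limb out and the two definitions still in conflict.

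A reader might go further and infer that worsening AEs vanish from the report, that safety monitoring is weakened, or that the first analysis is affected more strongly because it may hold only five subjects. The documents do not support these readings. The AEs are still listed. The halt rule in Protocol 3.6.1 does not use the treatment-emergent flag. SAP section 6 names safety data explicitly only for the second and third analyses.

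**Conclusion.** The conflict is real and nothing in the SAP resolves it. Followed as written, the SAP omits from its AE tables a fully dated pre-infusion AE that worsens, or becomes related, under its original record. For an affected subject, the loss is 10 percentage points in any-occurrence rows where the subject has no other treatment-emergent AE, and possibly an understated maximum grade where there is another AE of the same term.

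The size rests on two things: ten treated subjects, and an unknown number of AEs updated in place. No document gives a rate for such AEs, so the total effect may be nil. The became-related limb probably adds few cases, because an implausible time sequence is a named ground for calling an AE unrelated (Protocol 8.2.1.2).

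This is a mismatch worth correcting, with a partial effect on the safety tables. It does not bear on the efficacy results.

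**What to change.** 1. In SAP 8.4.1.1, add the second and third limbs of Protocol 9.6.5 in the protocol's own wording, and keep the existing rules for partial and missing dates.
2. State what the active phase of the study means, since neither document defines it. One option is from the start of the infusion to the subject's last study visit.
3. In SAP 8.4.1.2, list as non-treatment-emergent only those AEs that meet none of the three limbs.
4. Add one eCRF instruction: a post-infusion increase in grade of an ongoing AE is recorded with its date, either as a new record or as a dated update. Without that date the worsening limb cannot be programmed.

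The cost is a short SAP edit, one recording instruction and minor programming, with no new assessments. Treatment-emergent counts may rise slightly. Subject counts are not inflated by a split record, because SAP 8.4.1.2 counts each system organ class or preferred term once per subject.
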